8.1.3 Randomisation

If the subject meets the randomisation criterion as measured at Visit 13, then the subject will at Visit 14 be randomised into one of the two treatment arms using an IWRS randomisation session. A drug accountability session confirming dispensing of allocated trial products should also be performed when dispensing trial products.

First date of the randomised trial product (bolus insulin) must be recorded in the eCRF.

The subject must attend randomisation visit fasting. For definition of fasting, please see section 8.1.5.

Investigator must hand out the subject mealtime insulin dose adjustment guide and instruct subjects how to self-titrate (section 8.3.3 and Appendix A).

8.1.4 Phone contacts

Before any phone contact, both the investigator and subject should agree on the timing and direction of the call. The investigator remains responsible for ensuring that the phone contacts occur even if it is agreed that the subject should call the site. A phone contact may be converted to a site visit if needed.

8.1.5 Fasting visits

The subjects must attend the visits specified in the flowchart (section $\underline{2}$) in a fasting condition. Fasting is defined as at least eight hours without drink or food intake prior to the visit except for water.

Insulin dosing (including basal insulin) and medication which should be taken with or after a meal should be withheld until blood sampling has been performed. If a subject attends the visit non-fasting, then the subject's blood samples, meal test and body weight measurement must be rescheduled within the visit window and at Visit 14 before randomisation to trial product.

8.1.6 Rescheduled visits

The date of the rescheduled assessment in the eCRF should reflect the actual date of the rescheduled assessment (i.e. the actual visit date will differ from the assessment date under the same visit).

8.1.7 End of treatment

At end of treatment trial products must be discontinued and a completion IWRS session must be performed. Last date on the basal and bolus trial insulin must be recorded in eCRF.

| Protocol | Trial ID: NN1218-4113 | CONFIDENTIAL | Date: 28 March 2017 | Novo Nordisk | Version: 2.0 | Status: Final | Page: 34 of 113 |

The subject must be switched to a suitable marketed product at the discretion of the investigator and this product must be recorded on the concomitant medication (diabetes) form in eCRF, as described in section 8.2.6.

8.1.8 Follow-up period

The follow-up visit 1 (FU1) is a site visit and must take place 7-17 days after the end of treatment visit. Follow-up contact 2 (FU2) is a phone contact and must take place 30-35 days after the end of treatment visit.

Follow-up visit 1

The following data will be collected:

- AEs
- Concomitant medication
- Current diabetes medication
- Hypoglycaemic episodes
- Additional information on injection site reactions

Follow-up contact 2

The following data will be collected:

- AEs
- Concomitant medication
- Current diabetes medication
- Hypoglycaemic episodes

8.1.9 Premature discontinuation of trial products

If a subject prematurely discontinues trial products after randomisation (Visit 14), the investigator must undertake procedures similar to those for Visit 30 as soon as possible, also called Visit 30A (see flowchart section 2).

Premature discontinuation of trial products must be registered in the eDiary webportal. This must be performed at least 4 days prior to Visit 30A to ensure scheduling of the 7-9-7-point SMPG profile on the three days prior to Visit 30A. Subjects should perform this 7-9-7 point SMPG profile before discontinuing trial products.

At Visit 30A subjects must undergo the meal test before discontinuing trial products. The meal test should be performed with bolus trial insulin. If it is not feasible due to safety reasons including pregnancy as judged by the investigator the meal test should be performed with the marketed bolus product the subject is switched to.

Protocol		Date:	28 March 2017	Novo Nordisk
Trial ID: NN1218-4113	CONFIDENTIAL	Version:	2.0	
UTN: U1111-1180-0636	CONFIDENTIAL	Status:	Final	
EudraCT no.: 2016-000878-38		Page:	35 of 113	

The primary reason for premature discontinuation of trial products must be specified in the eCRF, and final drug accountability must be performed. A treatment discontinuation session must be made in the IWRS after the final meal test.

The subject should be switched to a suitable marketed product at the discretion of the investigator. The medication should be recorded on the concomitant medication (diabetes) form in the eCRF, as described in section 8.2.6 at each contact after trial product discontinuation.

The subject should also complete the follow-up visits (FU1 and FU2) 7 days and 30 days after discontinuation of trial product. Visit 31 (FU1) can be converted into a phone contact as the eDiary will not be collected at this visit for the subjects that discontinue trial products prematurely.

In addition, subjects prematurely discontinued from trial products should continue with the per protocol planned visits at 4 (Visit 18), 8 (Visit 22), 12 (Visit 26), 16 (Visit 30) weeks after randomisation depending on when the subject discontinues trial products. The meal test at Visit 30 should be done with the subjects' currently prescribed insulin treatment with the same bolus insulin dose as at baseline.

The following assessments are not applicable for subjects that prematurely discontinue trial products: 4 point profiles, daily doses of trial insulin, time of injection, dose recommendation, reason for deviation and collection of technical complaints.

In the following situations, only one visit should take place:

- If Visit 30A is within 2 weeks of one of the per protocol planned visits, only Visit 30A should be performed
- If any per protocol planned visit and the windows of a follow-up visit are overlapping according to visit schedule, only the per protocol planned visit should be performed

It should be documented in the medical records if subject refuses to attend a visit from Visit 30A and onwards.

The eDiary must be returned to the site at the last site visit (Visit 30).

A subject that permanently discontinues trial product before the End of Treatment visit (V30), will be considered to be a treatment non-completer.

For Argentina, Russia, Serbia and Ukraine: The BG meter should be collected by the investigator at the last scheduled site visit (Visit 30).

Protocol
Trial ID: NN1218-4113
CONFIDENTIAL
Date: 28 March 2017 | Novo Nordisk
Version: 2.0

Status:

Page:

Final

36 of 113

UTN: U1111-1180-0636 EudraCT no.: 2016-000878-38

eDiary records after premature discontinuation of trial products:

Date, actual clock time and value of the SMPG measurements performed as part of the 7-9-7-point profiles on the three consecutive days prior Visit 30A, Visit 22 and Visit 30 will be transferred to the eDiary, where each measurement should be assigned to the corresponding time point.

For hypoglycaemic episodes only a reduced amount of information should be recorded from one day after Visit 30A and to Visit 30 (see section 8.4.2):

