8.1.9 Premature discontinuation of trial products

If a subject prematurely discontinues trial products after randomisation (Visit 14), the investigator must undertake procedures similar to those for Visit 30 as soon as possible, also called Visit 30A (see flowchart section 2).

Premature discontinuation of trial products must be registered in IWRS. This must be performed at least 4 days prior to Visit 30A to ensure scheduling of the 7-9-7-point SMPG profile on the three days prior to Visit 30A. Subjects should perform this 7-9-7 point SMPG profile before discontinuing trial products.

At Visit 30A subjects must undergo the meal test before discontinuing trial products. The meal test should be performed with bolus trial insulin. If it is not feasible due to safety reasons including pregnancy as judged by the investigator the meal test should be performed with the marketed bolus product the subject is switched to.

The primary reason for premature discontinuation of trial products must be specified in the eCRF, and final drug accountability must be performed. A treatment discontinuation session must be made in the IWRS after the final meal test.

Protocol		Date:	23 February 2018	Novo Nordisk
Trial ID: NN1218-4113	CONFIDENTIAL	Version:	4.0	
UTN: U1111-1180-0636	CONFIDENTIAL	Status:	Final	
EudraCT no.: 2016-000878-38		Page:	36 of 112	

The subject should be switched to a suitable marketed product at the discretion of the investigator. The medication should be recorded on the concomitant medication (diabetes) form in the eCRF, as described in section 8.2.6 at each contact after trial product discontinuation.

The subject should also complete the follow-up visits (FU1 and FU2) 7 days and 30 days after discontinuation of trial product. Visit 31 (FU1) can be converted into a phone contact as the diary can be collected at the next site visit for the subjects that discontinue trial products prematurely.

In addition, subjects prematurely discontinued from trial products should continue with the per protocol planned visits at 4 (Visit 18), 8 (Visit 22), 12 (Visit 26), 16 (Visit 30) weeks after randomisation depending on when the subject discontinues trial products. The meal test at Visit 30 should be done with the subjects' currently prescribed insulin treatment with the same bolus insulin dose as at baseline.

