At the baseline meal test, the bolus insulin dose should be calculated by the investigator by dividing the digestible carbohydrate content of the standardised meal by a calculated insulin:carbohydrate ratio. The insulin:carbohydrate ratio in this trial is calculated by dividing 500 by the total daily dose (taken from the day before) of both basal and bolus insulin. The calculated dose should be rounded to the nearest whole unit.

Same bolus insulin dose will be used for the meal test at end of treatment. The insulin should be administered subcutaneously in the abdomen in accordance with Table 8–1.

Initiation of meal test

The subject's body weight must be measured before start and a blood sample must be drawn two minutes before intake of the standardised meal.

For the meal test at Visit 14 the subject must receive the bolus insulin that was also used in the runin period.

For the meal test at Visit 30 the subject should receive the bolus trial insulin they were randomised to and have used throughout the treatment period. If subject has been prematurely discontinued they should perform a meal test both at Visit 30A and again at Visit 30; the meal test at Visit 30 should be performed with the marketed bolus product the subject was switched to.

The start of consumption of the liquid meal is defined as time point 0. The subject must consume the liquid meal as quickly as possible and within 12 minutes. The investigator should confirm that the subject consumed the required volume of the standardised liquid meal in the eCRF.

Protocol Trial ID: NN1218-4113 UTN: U1111-1180-0636 EudraCT no.: 2016-000878-38

CONFIDENTIAL

 Date:
 23 February 2018

 Version:
 4.0

 Status:
 Final

 Page:
 43 of 112

Table 8–1 Meal test schedule

Time point (minutes)	Blood sample	SMPG values	Standardised meal	Bolus insulin injection
Before start of meal test		X (within target range 4.0-8.8 mmol/L [71-160 mg/dL])		
-2	X			
0			X	X Insulin injection at the start of the meal
30	X			
60	X	X (as appropriate to ensure		
120	X	subject's safety)		
180	X	1		
240	X	1		
End of meal test		X (for subject's safety)		

Conduct of meal test

The subject should stay in the clinic to have the blood samples drawn after 30 minutes, 1, 2, 3 and 4 hours from the start of the standardised meal, as detailed in Table 8–1. The samples will be analysed by the central laboratory.

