To compare the safety of faster aspart to NovoRapid® both in combination with insulin degludec with or without metformin in adults with T2DM treated with a basal-bolus regimen.

Subjects prematurely discontinued from trial product should continue with the per protocol planned visits at 4 (Visit 18), 8 (Visit 22), 12 (Visit 26), 16 (Visit 30) weeks after randomisation depending on when the subject discontinues trial products.

For further details on handling of subjects that prematurely discontinue from trial product and the trial in general, please see the trial protocol.

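### The two one-visit rules in Protocol 8.1.9 give opposite instructions for the same planned visit of an early stopper, and the first can waive Visit 30

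*Protocol*

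**What the plan says.** Section 8.1.9 of protocol version 4.0, unchanged on this point from version 2.0, lists two situations in which a single visit is to be held.

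- Bullet 1: "If Visit 30A is within 2 weeks of one of the per protocol planned visits, only Visit 30A should be performed".
- Bullet 2: "If any per protocol planned visit and the windows of a follow-up visit are overlapping according to visit schedule", then "only the per protocol planned visit should be performed".

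No order of precedence is given. The same section says that early stoppers "should continue with the per protocol planned visits at 4 (Visit 18), 8 (Visit 22), 12 (Visit 26), 16 (Visit 30) weeks after randomisation", qualified by when they stop. SAP 1.1 repeats this schedule with the same qualifier. Section 8.3.1 has no qualifier: early stoppers "should perform a meal test both at Visit 30A and again at Visit 30".

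Visit 30A carries procedures similar to those of Visit 30. Its meal test is normally done with trial insulin before stopping, whereas the Visit 30 meal test of an early stopper uses the marketed bolus product. The SAP (section 2, Visit reallocation) moves Visit 30A data to the next scheduled visit at which the assessment is planned. If two values then fall at the same visit, the reallocated on-treatment value serves the secondary estimand and is not used for the primary one.

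**The concern.** Planned visits are four weeks apart and FU1 falls 7 to 17 days after stopping. A planned visit can therefore be close enough to Visit 30A to trigger bullet 1 and also lie in the FU1 range that triggers bullet 2. A site that obeys one bullet then breaches the other, and sites may settle the matter differently.

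The second issue is Visit 30. The primary estimand is the week-16 difference regardless of treatment discontinuation, so an early stopper's own week-16 value is the one it needs. Bullet 1, read literally, tells sites not to collect that value after a late Visit 30A. The same holds for the week-16 meal test, which supplies confirmatory step 2. Version 4.0 also allows FU1 to become a phone contact because the diary "can be collected at the next site visit for the subjects that discontinue trial products prematurely". If Visit 30 is waived and FU1 is by phone, no later site visit remains.

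**Working it through.** The plan states no figure on this point, so there is none to reproduce. The check is a count of days.

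**Inputs**
- Planned visits after stopping: weeks 4, 8, 12 and 16, i.e. days 28, 56, 84 and 112 (8.1.9), each ±3 days (flow chart).
- FU1: 7 to 17 days after the end-of-treatment visit (8.1.8); for early stoppers it counts from discontinuation of trial product (8.1.9). I apply the same 10-day window to them.
- 10% stop treatment and half of these leave the trial (17.1); 1072 randomised.
- Assumptions: Visit 30A falls on the stopping day, and stopping days are uniform over days 0 to 111.

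**Conditions.** Let d be the day of Visit 30A, P the next planned visit and g = P − d.
- Bullet 1 applies if g ≤ 14: 14 of every 28 days, 56/112 = 50%.
- Bullet 2, planned visit at its nominal date: d + 7 ≤ P ≤ d + 17, so 7 ≤ g ≤ 17.
- Bullet 2, planned visit with its window: P + 3 ≥ d + 7 and P − 3 ≤ d + 17, so 4 ≤ g ≤ 20.

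**Both bullets apply**

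| Reading | Gaps g | Days | Share |
|---|---|---|---|
| Nominal date | 7 to 14 | 32/112 | 28.6% |
| With ±3 days | 4 to 14 | 44/112 | 39.3% |
| Nominal date, bullet 1 as under 14 days | 7 to 13 | 28/112 | 25.0% |
| With ±3 days, bullet 1 as under 14 days | 4 to 13 | 40/112 | 35.7% |

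Bullet 2 mentions only the follow-up visit's window, so the nominal-date reading is closer to its wording. The range is 25% to 39%.

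**What the site does in that zone**
- Bullet 1 first: the planned visit is not held, so nothing displaces FU1, and FU1 stands.
- Bullet 2 first: the planned visit is held and FU1 is dropped.
- Both waivers applied, ignoring bullet 2's instruction to hold the planned visit: neither takes place.

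**Visit 30.** Bullet 1 reaches Visit 30 when 112 − d ≤ 14, i.e. days 98 to 111: 14/112 = 12.5%.
- Days 109 to 111 lie inside the Visit 30 window (109 to 115), so Visit 30A is itself a timely week-16 assessment. That leaves days 98 to 108: 11/112.
- The on-treatment period runs to 7 days after the last dose. For a stop on day 105 or later, day 112 still counts as on-treatment. An off-treatment week-16 value is therefore lost only for days 98 to 104: 7/112.

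**Subjects.** 1072 × 0.10 × 0.5 = 53.6 stop but stay.
- Conflict zone: 53.6 × 32/112 = 15.3 to 53.6 × 44/112 = 21.1 (13.4 at 28/112).
- Visit 30 waived: 53.6 × 14/112 = 6.7; outside its own window: 53.6 × 11/112 = 5.3.
- Off-treatment week-16 value lost: 53.6 × 7/112 = 3.4.

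**Effect on the mean.** As an illustration, suppose all 6.7 subjects were in one arm and each value differed by the full 0.4-point margin. That arm's mean would move by 6.7 × 0.4/536 = 0.005 percentage points.

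**The case against.** A reader might infer that the two bullets together cancel both the planned visit and FU1 on 39% of stopping days. The text does not support that. Both bullets are introduced as cases in which one visit is held, and bullet 2 drops FU1 only while telling the site to perform the planned visit. Losing both requires applying half of bullet 2. The 39% also adds a planned-visit window that bullet 2 does not mention.

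A reader might also infer that week-16 data are lost for everyone who stops in the last two weeks. They are not: Visit 30A collects the same assessments and the SAP places them at week 16. Nor is safety follow-up lost. AEs are collected through FU2, which for these late stoppers lies clear of any planned visit, and FU1 is a site visit unless the site converts it.

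Finally, sparing a subject a second fasting visit is a legitimate choice. The meal test takes up to 6 hours with six blood samples, and repeating it the day after a day-111 Visit 30A would serve no purpose. The attendance statements in 8.1.9 and SAP 1.1 carry a timing qualifier, so they can be read as a general rule with exceptions.

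All of this stands, and it limits the point. It does not supply a precedence rule or give 8.3.1 an exception. Nor does it explain why bullet 1 should prevent collection of the value that the SAP prefers for the primary estimand when both exist.

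**Conclusion.** The two bullets contradict each other about whether the same planned visit takes place, on about 25% to 39% of stopping days, or 15 to 21 subjects on the two main readings. A site could end up dropping both visits, but the protocol does not require it.

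Bullet 1 also waives Visit 30 after a Visit 30A on days 98 to 111, against 8.3.1. For about 7 subjects the primary analysis would then use an on-treatment value up to 14 days early. For only about 3 of them is an off-treatment value, by the plan's own definition, lost. The consequence for mean HbA1c is negligible. The reason to act is consistent conduct across sites and agreement between the visit rules and the estimand.

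The counts rest on uniform stopping dates, Visit 30A on the stopping day, and the plan's assumed 10% discontinuation with half remaining in the trial. Later Visit 30A dates or clustered stopping would shift them.

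**What to change.** Reconcile the two bullets in 8.1.9 with each other and with 8.3.1.

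1. Waive a follow-up contact only if the overlapping planned visit is actually performed, and state whether overlap is judged on the planned visit's nominal date or on its ±3-day window.
2. Do not let bullet 1 waive the Visit 30 efficacy assessments unless Visit 30A itself falls within the Visit 30 window, and put the same exception into 8.3.1.

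This takes a few sentences. The first change costs almost nothing. The second means that about 5 subjects (days 98 to 108), or up to 7 if the in-window exception is not adopted, have a second visit within two weeks, possibly with a repeat meal test.

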8.1.10 Withdrawal from trial

If a subject withdraws consent, the investigator must aim to undertake procedures similar to those for Visit 30 including the meal test, as soon as possible, also called Visit 30A. The investigator must encourage the subjects to undergo the meal test at Visit 30A. The meal test must be performed with bolus trial insulin according to randomisation. If it is not feasible due to safety reasons including pregnancy as judged by the investigator the meal test should be performed with the marketed bolus product the subject is switched to.

If the subject agrees, the investigator must aim to perform the follow up visits (FU1 and FU2) 7 and 30 days after discontinuation of trial product.

In case a premature discontinuation of trial product subject chooses to withdraw consent from trial after completing Visit 30A, FU1 and FU2, the investigator must encourage the subjects to undergo procedures of Visit 30, as soon as possible, whereas FU1 and FU2 are not to be completed again.

The end of treatment and end of trial form in the eCRF must be completed, and final drug accountability must be performed even if the subject is not able to come to the trial site. A treatment discontinuation session must be made in the IWRS. The case book must be signed.

Although a subject is not obliged to give his/her reason(s) for withdrawing consent, the investigator must make a reasonable effort to ascertain the reason(s), while fully respecting the subject's rights. Where the reasons are obtained, the primary reason for withdrawing consent must be specified in the eCRF.

A subject that is withdrawn from trial before the End of Treatment Visit (V30), will be considered to be a treatment non-completer and a trial non-completer.

 Protocol
 Date:
 28 March 2017
 Novo Nordisk

 Trial ID: NN1218-4113
 Version:
 2.0

 UTN: U1111-1180-0636
 Status:
 Final

Page:

37 of 113

8.1.10.1 Lost to follow-up

EudraCT no.: 2016-000878-38

The following actions must be taken in relation to a subject who fails to attend the site for a required visit:

- The site must attempt to contact the subject and reschedule the missed visit as soon as possible
- The site must re-train the subject in the importance of maintaining the scheduled visits

In cases in which the subject is deemed lost to follow-up the investigator must make every effort to regain contact with the subject (e.g. telephone calls to friends or family members, e-mails or certified letter to the subject as applicable). These contact attempts must be documented in the subject's medical records. Should the subject continue to be unreachable, only then will he/she be considered to have withdrawn from the trial with the primary reason being "lost to follow-up".

8.1.11 Review of results

Review of ECG results, eye examination report, laboratory reports, data entered in the eDiaries etc. must be documented either on the documents, printouts, in the eDiary webportal or in the subject's medical record.

If clarification of entries or discrepancies in the eDiary is needed, the subject must be questioned and a conclusion made in the subject's medical record. Care must be taken not to bias the subject. Any discrepancies or missing data points available elsewhere related to a 7-9-7 point profile or hypoglycaemic episodes must be corrected or added.

